**CCI**

**CCI**

## 5.3 Selection of Trial Population

Only persons meeting all inclusion criteria and no exclusion criteria may be enrolled into the trial as patients. Prior to performing any trial assessments not part of the patient's routine medical care, the Investigator will ensure that the patient or the patient's legal representative has provided written informed consent following the procedure described in Section 9.2.

### 5.3.1 Inclusion Criteria

1. Must voluntarily give written informed consent. Patients must read and fully understand the Informed Consent Form (ICF) and the requirements of the trial and must be willing to comply with all trial visits and assessments.
2. Moderately to severely active diagnosis of RA with disease duration of at least 6 months from confirmed diagnosis, as defined by the 2010 revised ACR/EULAR 2010 criteria or the 1987 ARA criteria (Criteria of American Rheumatology Association) (present or past).
3. Have moderately to severely active disease despite MTX therapy defined as:
  - a.  $\geq 6$  swollen joints and  $\geq 6$  tender joints (from the 66/68 joint count system) at screening and randomization.
  - b. Either ESR (Westergren)  $\geq 28$  mm/h or serum CRP  $\geq 1.0$  mg/dL at screening.
4. Must have been treated with MTX for a total of at least 12 weeks prior to baseline and must have been on both: a stable route of administration (oral or parenteral) and stable dose of MTX (10 to 25 mg/week) for at least 4 weeks prior to screening.
5. Age 18 and older.
6. Must be adalimumab naïve and must not have received a non-marketed experimental biological agent for their RA in the past, or any biological agent not belonging to the class of TNF inhibitors. Patients who have received no more than 1 TNF inhibitor (either originator or investigational biosimilar candidate that underwent comparison with EU or US reference compounds) other than adalimumab are allowed to participate in the trial.
7. Must have discontinued infliximab (either originator or investigational or approved biosimilar), certolizumab pegol (either originator or investigational or approved biosimilar) or golimumab (either originator or investigational or approved biosimilar) 8 weeks prior to screening, or etanercept (either originator or investigational or approved biosimilar) 4 weeks prior screening.
8. A female patient is eligible to participate if she is not pregnant (see [Appendix A](#)), not breast feeding, and at least one of the following conditions applies:
  - a. Not a woman of childbearing potential (WOCBP) as defined in [Appendix A](#)

OR

- b. A WOCBP who agrees to use a highly effective contraception (ie, methods with a failure rate of less than 1% per year) as detailed in [Appendix A](#) of this protocol 3 months before the start of the first dose of the IMP, during the treatment period, and for at least 5 months after the last dose of the IMP.
9. Female patients must not be pregnant and if of childbearing potential, must have a negative serum pregnancy test at screening and a negative urine pregnancy test at baseline before randomization.
10. Female patients must not be lactating or breast-feeding at screening through at least 5 months after the last treatment with IMP.
11. Male patients must be either surgically sterile (vasectomy with documented confirmation of aspermia) or must agree to use a condom and have their female partners use a highly effective contraception (ie, methods with a failure rate of less than 1% per year) as detailed in [Appendix A](#) for 3 months before the first dose of IMP, during the treatment period and for at least 5 months after the last dose of IMP, unless their partners are infertile or surgically sterile. Male patients must agree to continue to practice adequate contraception for 5 months after the administration of the IMP and refrain from donating sperm during this period.
12. Patient must be able and willing to self-administer s.c. injections.

### 5.3.2 Exclusion Criteria

1. ACR functional class IV as defined by the ACR classification of functional status or wheelchair/bedbound.
2. A diagnosis of Felty's syndrome.
3. A diagnosis of any other inflammatory arthritides/systemic autoimmune disease other than secondary Sjögren's syndrome.
4. Received therapy with leflunomide within 12 weeks prior to baseline unless patient has undergone a drug elimination procedure with cholestyramine or activated charcoal powder, in which case the wash-out period is a minimum of 4 weeks.
5. Received DMARDs other than MTX including but not limited to oral or injectable gold, sulfasalazine, azathioprine, penicillamine, cyclosporine, or tacrolimus within 4 weeks prior to baseline. Patients may be taking oral hydroxychloroquine provided that the dose is not greater than 400 mg/day, or chloroquine provided that the dose is not greater than 250 mg/day and that doses have been stable for a minimum of 12 weeks prior to baseline. The hydroxychloroquine or chloroquine treatment will need to be continued at a stable dose for the duration of the study.

6. Received increasing doses of Non-Steroidal Anti-Inflammatory Drugs (NSAIDs) (including low dose aspirin and COX-2 inhibitors) in the 2 weeks prior to baseline.
7. Prior exposure to alkylating agents, such as chlorambucil or cyclophosphamide.
8. Use oral glucocorticoids > 10 mg/day prednisone or equivalent. Doses up to 10 mg/day are allowed if have been kept stable for the 4 weeks prior to baseline.
9. Any intra-articular, intravenous, or intramuscular use of corticosteroids in the 6 weeks prior to baseline.
10. High potency opioid analgesics (eg, methadone, hydromorphone, oxycodone, fentanyl, or morphine) are prohibited during the study; other analgesics are allowed (eg, propoxyphene, tramadol, codeine, or aspirin), although not within 12 hours of study visits.
11. History of tuberculosis (TB), presence of active tuberculosis, or latent tuberculosis as detected by imaging (eg, chest X-ray, chest Computerized Tomography [CT] scan, Magnetic Resonance Imaging [MRI]) and/or positive QuantiFERON-TB Gold test (QFT) and/or clinical examination or has had latent TB disease at any time in the past.

Patients will be evaluated for latent TB infection (LTBI) by the QFT enzyme-linked immunosorbent assay and by chest X-ray. If a patient tests positive for LTBI at screening, the patient will be screen failed and will not be randomized. Patients with indeterminate QFT test result may be re-tested once within the screening period:

- i. If the re-test is negative, the patient is eligible to take part in the trial.
- ii. If the re-test is positive, the patient will not be eligible to participate in the trial.
- iii. If the re-test is again indeterminate, the patient will be considered as having LTBI and will not be eligible to participate in the trial. No further QFT will be performed.
12. Received a live vaccine within 3 months prior to IMP administration or intends to receive a live vaccination during the trial or within 3 months after the last dose of IMP.
13. History of hypersensitivity to any component of the IMP formulation, comparable drugs, or latex.
14. Any infection as follows:
  - a. Requires treatment with oral antibiotics within 14 days prior to IMP administration.
  - b. A serious infection defined as requiring hospitalization or treatment with intravenous antibiotics within 8 weeks prior to IMP administration.

- c. Has had herpes zoster or any opportunistic infection (eg, histoplasmosis, coccidioidomycosis, blastomycosis, pneumocystis, listeriosis, legionellosis, or parasitic infections) within 6 months prior to administration of IMP.
- d. A history of persistent chronic infection or recurrent infections (3 or more of the same type of infection in any rolling 12 month period, eg, urinary tract or upper respiratory tract infections).
- e. Have documentation of seropositivity for human immunodeficiency virus (HIV), or positive hepatitis C antibody test or hepatitis B surface antigen test and/or core antibody test for IgG and/or IgM or total Ig at screening.

15. History of lymphoproliferative disease or previous malignancy. Curatively treated basal or squamous cell carcinoma of the skin is not excluded, unless it occurred within 12 months of randomization. Curatively treated localized in situ carcinoma of the cervix is also not excluded, if there is no evidence of recurrence within the last 5 years prior to randomization.

16. Has a poorly controlled medical condition, such as but not limited to, poorly controlled diabetes, unstable ischemic heart disease, uncontrolled hypertension (systolic  $\geq$  160 mmHg and/or diastolic  $\geq$  95 mmHg), or other relevant medical disease, such as a neurological, pulmonary, gastrointestinal, or endocrine disease or a history of clinically significant hematological, renal, or liver disease or any other condition that, in the opinion of the Investigator, would put the patient at risk by participation in the trial.

17. Any major surgery (including arthroplasty) performed within the 6 weeks prior to the first dose of IMP.

18. Have presence of a solid organ or bone marrow transplant (with the exception of a successful corneal transplant  $>$  3 months prior to screening).

19. Have a concomitant diagnosis or history of congestive heart failure (New York Heart Association [NYHA] class III or IV).

20. Have a known history, family history of or symptoms consistent with a demyelinating disease, such as multiple sclerosis, or optic neuritis, or symptoms suggestive of such a disorder.

21. Laboratory abnormalities deemed clinically significant by the Investigator or any of the following at screening:

- a. Hemoglobin  $<$  8 g/dL for women or 8.5 g/dL for men.
- b. White blood cells (WBCs)  $<$  3.5  $\times$  10^9/L.
- c. Absolute neutrophil count (ANC)  $<$  1.5  $\times$  10^9/L.
- d. Platelet count  $<$  100  $\times$  10^9/L.

- e. Alanine aminotransferase (ALT) or aspartate aminotransferase (AST) > 2 times the upper limit of normal.
- f. Creatinine > 1.5 mg/dL if < 65 years old, or > upper limit of normal if  $\geq$  65 or with proteinuria 4+ or greater by dipstick.

22. Women who are pregnant, lactating, or planning pregnancy within 6 months after the last dose of IMP.
23. Legal incapacity or limited legal capacity.
24. Patient is considered by the Investigator, for any reason, to be an unsuitable candidate for the trial.
25. Patient has participated in any nonbiological investigational clinical trial within 12 weeks or 5 drug half-lives (whichever is longer) before first administration of IMP in this trial or planned intake of an investigational drug during the course of this trial.
26. History of clinically significant drug or alcohol abuse within the last 2 years.

## **5.4 Criteria for Patient Withdrawal**

### **5.4.1 Withdrawal from Trial Therapy**

A patient will no longer receive the study medication in the event of any of the following circumstances:

- a. Any events that unacceptably endanger the safety of the patient, including but not limited to the following:
  - Use of prohibited treatment that in the opinion of the Investigator or Sponsor necessitates the patient treatment to be interrupted
  - Occurrence of an exclusion criterion that is clinically relevant and affects the patient's safety, if discontinuation is considered necessary by the Investigator and/or Sponsor
  - Anaphylactic or other serious allergic reactions
  - Development of active or latent TB
  - New or worsening symptoms of congestive heart failure
  - Biopsy confirmation of any malignancy other than non-melanoma skin cancer, such as basal cell carcinoma and squamous cell carcinoma.
  - Symptoms suggestive of lupus-like syndrome
  - Pregnancy
- b. Interruption of MTX more than twice in a period of 4 weeks, or for a period of interruption longer than 4 months.

- c. Noncompliance or protocol violations that in the opinion of the Investigator or Sponsor necessitates the patient being withdrawn. The decision to withdraw the patient should be taken in consultation with the Medical Monitor.
- d. Participation in any other trial during the duration of this trial.
- e. If the whole trial is discontinued prematurely.
- f. Lost to follow-up.

If a patient is lost to follow-up, every possible effort must be made by trial center personnel to contact the patient and determine the reason for discontinuation. The measures taken to follow-up must be documented. If a patient discontinues before completion of trial procedures, the reason for discontinuation must be documented in the CRF and source documents.

Patients who discontinue from study medication (but continue safety/immunogenicity visits) before the Week 52 visit will immediately complete an Early Termination visit and return for a Safety/Follow-up visit 4 weeks after the last dose of IMP. During this 4-week Safety Follow-up period, no excluded treatment for RA (as defined in this protocol) should be administered. Subjects will return for an additional safety visit 4 months after the last dose of IMP. Treatment for RA from the 4-week Safety Follow-up visit to the 4-month Safety Evaluation visit will be at the discretion of the Investigator following institutional standard of care. The 4-week and 4-month safety Follow-up visits will not be duplicated if either of these visits falls within 2 weeks of an otherwise scheduled visit. If the 4-week and 4-month safety Follow-up visit since last IMP are completed within the 52 week visit schedule, these will not be repeated thereafter.

Withdrawn patients will not be replaced.

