### 5.2.1 Scientific Rationale for Study Design

A double-blind, two-arm, parallel-group design represents an ideal setting to provide comparative long-term immunogenicity and safety data for the new [CCI](#) formulation versus Humira®.

Regulatory agencies are aware of the difficulty to power for safety and immunogenicity.

According to EMA “the investigation of safety is a multidimensional problem. Although some specific adverse effects can usually be anticipated and specifically monitored for any drug, the range of possible adverse effects is very large, and new and unforeseeable effects are always possible. Further, an adverse event (AE) experienced after a protocol violation, such as use of an excluded medication, may introduce a bias. This background underlies the statistical difficulties associated with the analytical evaluation of safety and tolerability of drugs, and means that conclusive information from confirmatory clinical trials is the exception rather than the rule. In most trials the safety implications are best addressed by applying descriptive statistical methods to the data, supplemented by calculation of confidence intervals wherever this aids interpretation.” [\(20\)](#).

Concerning immunogenicity assessment, regulatory agencies currently prefer to focus on a comprehensive, yet descriptive, presentation and correlation of the immunogenicity data generated in clinical studies [\(21, 22, 23, 24, 25\)](#).

According to regulatory guidance and literature, data captured in the study should allow exploration of the possible correlation of the immunogenicity assessment to PK (eg,  $C_{trough}$ ), safety (eg, injection site reactions), and/or efficacy (eg, reduced or loss of clinical response) [\(26, 27\)](#). In addition, the kinetics of an immune response (time to anti-drug antibodies [ADA], titer over time, persistent or transient ADA) observed will be used to compare the proposed biosimilar with the reference product to contribute to the totality of evidence and to the biosimilarity claim.

For all these reasons, the proposed study cannot be powered to demonstrate equivalence in safety and immunogenicity.

In this study, RA patients must have active disease, and be inadequate responders to methotrexate (MTX). The patients will continue to use MTX at a stable dose in combination with adalimumab

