#### 6.4.1 Permitted Medicines

Permitted medicines will not be provided by the sponsor as they are considered standard of care background medications.

It is important that medication dosages taken during the study period remain stable. This includes, but it is not limited to, the dosage of corticosteroids and NSAIDs. However, reductions in these treatments will be allowed as clinically required for safety reasons.

**Methotrexate:** All patient should maintain a stable MTX dose (10 to 25 mg/week, PO, IM, or SC) during the study period. Any modification of the route of administration is not allowed. However, a dose reduction of MTX will be allowed in case of AEs. Temporary interruptions administration are allowed for up to 14 days (can be interrupted up to twice because MTX is administered once weekly). See withdrawal criteria related to interruptions in Section 5.4.1.

**Folic Acid:** It is possible that certain AEs that are commonly associated with MTX treatment occur. In order to minimize MTX toxicity, all patients treated with MTX should receive folic acid or equivalent at a dose of at least 5 mg/week according to local guidelines. This can either be given

as a single dose weekly or be divided into daily doses to achieve at least 5 mg folic acid per week. It is the Investigator's decision as to which dosing regimen is used.

**Hydroxychloroquine or chloroquine:** as per inclusion and exclusion criteria.

Oral corticosteroids ( $\leq 10$  mg/day prednisone or equivalent) and NSAIDs are permitted during the study.

**NSAID:** patients may be treated with NSAIDs (including low dose aspirin and COX-2 inhibitors) for symptomatic treatment of their arthritis up to the maximum recommended dose per local labeling throughout the study (including COX-2 inhibitors). Drug must be at a stable dose for at least 2 weeks prior to baseline. Increases in the NSAID dose during the study are not allowed. However, discontinuation or reduction is allowed in case of NSAID-related toxicity. In patients who receive NSAIDs, prophylactic treatment with proton pump inhibitors or H2-receptor blockers is recommended.

NSAIDS, up to the maximum recommended dose per local labeling, are also allowed for the management of AEs not related to RA such as colds or sprains throughout the study (including COX-2 inhibitors).

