### 8.3.2 Secondary Endpoints

#### Key Secondary Endpoint

- Efficacy
  - ACR20 at Week 12

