11.8 Data Derivation

The following conversion factors will be used to convert days to months or years, where applicable:

- 1 month = 30.4375 days
- 1 year = 365.25 days.

See Section 12.2 for the calculation of subject age.

Duration will be calculated by the difference of start and stop date + 1 (eg AE duration (days) = stop date of AE – start date of AE + 1) (if not otherwise specified). Durations are calculated only when both dates are available (imputed dates cannot be used for the duration computation).

See Section 14 for the calculation of treatment duration.

The time since an event (eg time since first diagnosis) will be calculated as reference date minus date of event.

12 Trial Subjects

The subsections in this section include specifications for reporting subject disposition and treatment/study discontinuations. Additionally, procedures for reporting protocol deviations are provided.

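### Protocol 5.4.1(b) leaves methotrexate interruption undefined, and its two withdrawal limbs do not fit together or with the 14-day allowance in 6.4.1

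*Protocol*

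**What the plan says.** Three parts of the protocol bear on background MTX.

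- **Design intent (5.2.1).** "The patients will continue to use MTX at a stable dose in combination with adalimumab", and this holds for the whole study.
- **Permission (6.4.1).** "Temporary interruptions administration are allowed for up to 14 days (can be interrupted up to twice because MTX is administered once weekly". The section then points onward: "See withdrawal criteria related to interruptions in Section 5.4.1".
- **Withdrawal (5.4.1).** The list opens with "A patient will no longer receive the study medication in the event of any of the following circumstances", so any single item suffices. Item (b) is "Interruption of MTX more than twice in a period of 4 weeks, or for a period of interruption longer than 4 months". Item (c) adds a discretionary route: "Noncompliance or protocol violations that in the opinion of the Investigator or Sponsor necessitates the patient being withdrawn", to be decided in consultation with the Medical Monitor.

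Three parts of the SAP depend on who meets a withdrawal criterion or stops early.

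- Section 10.1 counts a patient who meets a withdrawal criterion but is kept on as an important deviation.
- Section 10.2.3 excludes from the per-protocol set patients who drop out before Week 12. The compliance rule printed there concerns the investigational product, not MTX. Detailed criteria are in Appendix I, which is not among the pages supplied for review.
- Section 11.4.1 includes an ACR20 analysis in which patients who discontinue before Week 12 are imputed as non-responders.

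**The concern.** The permission and the stopping rule are meant to be read together, since one cites the other. Read together, they do not yield one rule. Section 6.4.1 speaks of 14 days and of two interruptions. Section 5.4.1(b) speaks of more than two interruptions in 4 weeks and, separately, of a single interruption longer than 4 months. Nothing says whether an interruption is one missed weekly dose or one continuous gap.

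This is an operative stopping rule. It decides who stops the study drug and goes at once to an Early Termination visit. Two sites can apply it in good faith to the same MTX record and reach opposite results, and the SAP rules listed above carry that difference into the deviation listing and the ACR20 analyses. The key secondary endpoint, "ACR20 at Week 12", falls inside the period in which the two readings diverge.

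**Working it through.** **Inputs**

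- Allowance: 14 days, MTX once weekly (Protocol 6.4.1).
- First limb: more than 2 interruptions in 4 weeks. Second limb: an interruption longer than 4 months. Either suffices (Protocol 5.4.1).
- Month length: "1 month = 30.4375 days" (SAP 11.8).
- Key efficacy visit: Week 12, that is 12 × 7 = 84 days.

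**Step 1. Reproduce the plan's own equivalence.** 14 days ÷ 7 days per dose = 2 weekly doses. This agrees with 6.4.1, where two interruptions correspond to two missed doses.

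**Step 2. Put the second limb on the same scale.** 4 × 30.4375 = 121.75 days; 121.75 ÷ 7 = 17.4 weeks. Against Week 12: 121.75 ÷ 84 = 1.45. Against the allowance: 121.75 ÷ 14 = 8.7. With 28-day months it would be 112 days, or 16 weeks, still longer than 12.

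**Step 3. Apply the first limb under each way of counting.** All 2^12 = 4,096 patterns of taken and missed doses over 12 weekly doses were examined. A 4-week period was taken to contain either 4 or 5 scheduled doses.

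| | Each missed dose is an interruption | Each continuous episode is an interruption |
|---|---|---|
| First limb is met | at the third missed dose in 4 weeks | never with 4 doses in the window (at most 2 episodes fit); with 5 doses, only if missed and taken doses alternate (3 episodes) |
| Longest lapse before Week 12 with no mandatory withdrawal | 2 doses | 12 doses |
| Most doses missed before Week 12 with no mandatory withdrawal | 6 of 12 | 12 of 12 |
| Role of the 4-month limb | none; the first limb is always met earlier | the only limb that acts on a continuous lapse, at 17.4 weeks |

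The 6 of 12 follows directly. Three consecutive 4-dose blocks with at most 2 missed doses each give 3 × 2 = 6, and repeating two missed, two taken achieves it.

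**Step 4. One patient, two outcomes.** Take a continuous lapse of 5 weekly doses, or 35 days.

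- Against 6.4.1: 35 > 14, so it is outside the allowance on either reading.
- Counting doses: at least 4 missed doses in a 4-week period, and 4 > 2, so study medication must stop.
- Counting episodes: 1 episode, not more than 2; 35 < 121.75 days. Neither limb of 5.4.1(b) is met.

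**Step 5. Follow it into the SAP.** Suppose the lapse is before Week 12. If the patient is kept on, 10.1 makes this an important deviation on the first reading, because a withdrawal criterion was ignored; on the second reading that entry does not apply. If the patient is stopped, and stopping study drug is treated as dropping out or discontinuing, 10.2.3 removes the patient from the per-protocol set and the withdrawal analysis in 11.4.1 sets ACR20 to non-response.

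**The case against.** The strongest reply is that the documents already show how to count. Section 6.4.1 ties two interruptions to 14 days because MTX is weekly, which treats each missed dose as one interruption. Carried into 5.4.1(b), two missed doses are allowed, a third within 4 weeks stops treatment, and the allowance and first limb agree. This has force, and it is the more natural reading of 6.4.1. It does not close the matter, because it leaves the 4-month limb with nothing to do. A site that assumes every clause has a purpose has real grounds for counting episodes.

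Three further replies stand and limit the point.

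- A reader might infer that withdrawal is triggered only beyond 4 months, so that MTX may lapse through the whole 12-week efficacy period. The documents do not support that. The first limb is joined by *or* and suffices alone. A 12-week lapse escapes mandatory withdrawal only if episodes are counted. Even then it breaches 6.4.1 and is open to discretionary withdrawal under 5.4.1(c), so it is untriggered, not permitted.
- A reader might also treat 14 days against 4 months as a contradiction in itself. A permitted limit shorter than a mandatory stopping limit is coherent. The fault is that the two limbs of 5.4.1(b) cannot both function.
- The analytical reach is bounded. The primary endpoint and immunogenicity use the Safety set, so per-protocol membership does not touch them. The key secondary analysis is descriptive and is also run on ITT. Appendix I may already hold an MTX code, so no gap in the per-protocol definition can be claimed.

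**Conclusion.** The inconsistency is real and should be corrected. *Interruption* is undefined, and under either way of counting one limb of 5.4.1(b) is idle or nearly so. The readings differ by a wide margin: the longest lapse without mandatory withdrawal is 2 weekly doses on one, and up to 17.4 weeks on the other.

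The conclusion rests on weekly MTX dosing as stated in 6.4.1 and on the SAP's month length; the 28-day alternative does not change it. The effects on the per-protocol set and on the imputation also assume that a mandatory stop of study drug counts as drop-out or discontinuation, which the SAP sections cited do not spell out. No document gives the frequency or clinical effect of MTX interruption, so neither the number of patients affected nor any shift in ACR20 can be estimated. Which limit was intended cannot be told from the text.

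**What to change.** Reconcile Protocol 5.4.1(b) and 6.4.1 into one consistent statement that covers:

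- what counts as an interruption (a missed weekly dose or a continuous episode);
- the permitted interruption, and whether the allowance applies per episode or over the whole study;
- the withdrawal trigger, worded so that each limb has a function or the redundant one is removed.

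The limits themselves are for the sponsor's clinical team; none is proposed here.

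In the SAP, check Appendix I for an existing MTX deviation code and align it with the reconciled wording, or add one if there is none. State whether stopping study drug under 5.4.1 counts as drop-out in 10.2.3 and as discontinuation in 11.4.1. Settle the counting rule no later than the data review meeting before database lock, while treatment is still blinded.

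The cost is one protocol clarification and, at most, one deviation code. Protocol 6.4 already requires changes to concomitant medication to be recorded in the CRF, so no new data collection should be needed.
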